6.2.2. Day 1 Assessments

After confirmation of eligibility has been evaluated, the following tests and procedures must be completed prior to enrollment and dosing/dispensing on Day 1:

- Reconfirm eligibility
- Perform complete physical examination
- Tanner Pubertal Stage Assessment
- Vital signs
- Body weight and height
- Biological parental height, unless unknown (eg, subject adopted, biological parent (s) deceased), will be collected at screening up to Day 1 visit.
- A single X-ray of the left wrist, hand, and fingers for Bone Age Assessment
- Assessment of AEs and concomitant medications
- Perform transient elastography (if available); if not performed at screening
- Pregnancy prevention counseling including partner pregnancy prevention for male participants (all subjects \geq 12 years of age and subjects $<$ 12 years of age at the discretion of the investigator based on subject's pubertal status)
- Ask subject and/or parent/legal guardian if the subject is able to swallow and tolerate taking pills. Perform SOF/VEL FDC swallowability assessment if not performed at screening.
- SOF/VEL Acceptability Questionnaires
- Quality of life survey: Subject is to review questionnaire and write/mark answers directly onto the questionnaire. Parent/legal guardian completes the parent/guardian questionnaire.

- Obtain blood samples for:
 - Hematology
 - Chemistry
 - Coagulation tests
 - HCV RNA
 - IL28B Genotype
 - Viral sequencing (archive)

— CCI

- Obtain urine samples for the following procedures:
 - Urinalysis
 - Urine pregnancy test for females of childbearing potential only

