6.2.2.1. Drug Administration

The following procedures/assessments are to be completed at this visit:

- Perform SOF/VEL FDC swallowability assessment (if not previously completed at screening).
- Dispense study drug(s) as directed by the IWRS
- Instruct the subject on the packaging, storage, administration of study drug, and provide dosing diary and instructions.
- Observe the subject taking the first dose of study drug (with or without food) and record the time of first dose.
- Subject or parent/legal guardian (as applicable) will complete the relevant acceptability questionnaires.

• CCI

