6.10.7. Acceptability Assessment

- Swallowability:

A SOF/VEL FDC swallowability assessment for the tablet formulation will be performed at screening up to Day 1.

12 to < 18 years of age:

Subjects who have indicated that they can take pills will be observed taking a placebo to match the 400/100 mg SOF/VEL FDC tablet. This will confirm the swallowability of the 400/100mg tablet formulation size.

- If a subject is unable to swallow the 400/100 mg SOF/VEL FDC placebo tablet, the subject will repeat the assessment with a placebo to assess swallowability of the 200/50 mg SOF/VEL FDC tablet.
- If unable to swallow the 200/50 mg low dose SOF/VEL FDC tablet, the subject will be assigned to SOF/VEL FDC oral granules formulation.

6 to < 12 years of age:

Subjects who have indicated that they can take pills will be observed taking a placebo to match the 200/50 mg low dose SOF/VEL tablet. This will confirm the swallowability of the 200/50 mg tablet size.

- If a subject is unable to swallow the 200/50 mg SOF/VEL low dose placebo tablet, the subject will be assigned to SOF/VEL FDC oral granules formulation.

3 to < 6 years of age:

Subjects will be administered SOF/VEL oral granules. There will not be any placebo provided to assess swallowability for this formulation.

Acceptability and palatability:

For all age groups, a questionnaire will be administered to subjects to assess acceptability and palatability of the formulation they received on Day 1, Week 12 and Early Termination (as applicable). If the subject is unable to complete the questionnaires, the parent/legal guardian will assist to complete the questionnaire on their behalf. The subject's parent/legal guardian will also complete a questionnaire on Week 12 or Early Termination (as applicable) for their assessment of acceptability of the formulation the subject received.

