Appendix 2. Study Procedures Table

Appendix Table 1. PK Lead-in: Screening and On-Treatment Study Visits

	Screening (-28 days)	On-treatment		
		Day 1 ⁱ	Day 3 Telephone call	Day 7 (+ 3 days)
Clinical Assessments				
Informed Consent / Assent	X			
Determine Eligibility	X	X		
Medical History	X			
Parental Height	X ^a	X ^a		
Complete Physical Examination	X	X		
Symptom-directed Physical Examination				X
Tanner Pubertal Stage Assessment ^b		X		
Vital Signs ^c	X	X		X
Body Weight and Height ^d	X	X		X
Bone Age Assessment		X		
AEs and Concomitant Medications	X	X	X	X
Transient Elastography, if available	X ^e	X ^e		
Pregnancy Prevention Counseling ^f		X		
SOF/VEL Swallowability Assessment	X ^g	X ^g		
SOF/VEL Acceptability Questionnaires		X		
Quality of Life Survey		X ^h		
Review of Study Medication Compliance				X
Study Drug Dispensing ⁱ		X		
Subject Dosing Diary ^j		X	X	X
Laboratory Assessments				
Hematology, Chemistry, Coagulation	X	X		X
HbA1c, Fibrotest [®] , APRI	X			
TSH	X			
Alpha-1 anti-trypsin	X			

	Screening (-28 days)	On-treatment		
		Day 1 ⁱ	Day 3 Telephone call	Day 7 (+ 3 days)
HIV testing, HCV antibody, HBsAg, HBsAb, HBcAb, and HAV antibody	X			
HBV DNA ^k	X			
HCV RNA	X	X		X
HCV Genotyping	X			
Viral Sequencing ^l		X		X
Serum or Urine Pregnancy Testing ^m	X	X		X
IL28B Genotyping		X		
Urinalysis	X	X		X
Urine Drug Screen	X			
CCI				
Intensive PK				X ^o

- a Biological parental height, if not collected at Day 1.
- b If the assessment determines that the subject is at a Tanner 5 at Day 1, no further Tanner Pubertal Stage Assessments are to be completed.
- c Vital signs include blood pressure, pulse, respiratory rate and temperature.
- d Height should be without shoes and should be collected by the same personnel, if possible.
- e May be performed at Screening up to Day 1.
- f Including partner pregnancy prevention for male participants (all subjects \geq 12 years old and subjects < 12 years old at the discretion of the investigator based on subject's pubertal status).
- g Swallowability can occur at Day 1 if not completed during screening.
- h Quality of life survey will be completed by all subjects and their parent/legal guardian. Subject and parent/legal guardian is to review questionnaire and write/mark answers directly onto the questionnaire.
- i Day 1 assessments must be performed prior to dosing. The IWRS system will provide direction on the specifics of each subject's study drug dispensing.
- j **CCI**

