### 3.7.3. Selection of Data in the Event of Multiple Records in an Analysis Window

Depending on the statistical analysis method, single values may be required for each analysis window. For example, change from baseline by visit usually requires a single value, whereas a time-to-event analysis would not require 1 value per analysis window.

If multiple valid nonmissing numeric observations exist in an analysis window, records will be chosen based on the following rules if a single value is needed:

- For baseline, the last available record on or prior to the date of the first dose of study drug will be selected. If there are multiple records with the same time or no time recorded on the same day, average (arithmetic mean) will be used for the baseline value.
- For postbaseline visits:

The record closest to the nominal day for that visit will be selected except for HCV RNA posttreatment follow-up visits, for which the latest record in the analysis window will be selected.

If there are 2 records that are equidistant from the nominal day, the later record will be selected.

If there is more than 1 record on the selected day, the average will be taken, unless otherwise specified.

If multiple valid nonmissing categorical observations exist in a window, records will be selected as follows:

- For baseline, the last available record on or prior to the date of the first dose of study drug will be selected. If there are multiple records with the same time or no time recorded on the same day, the value with the lowest severity will be selected (eg, normal will be selected over abnormal).
- For postbaseline visits, follow the same rules described above for postbaseline numeric observations, except that if there are multiple records on the same day, the most conservative value will be selected (eg, abnormal will be selected over normal).

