#### **7.10. Acceptability and Palatability of SOF/VEL FDC**

A questionnaire will be administered to subjects to assess acceptability and palatability of the formulation they received on Day 1, Week 12 and Early Termination (as applicable). If the subject is unable to complete the questionnaires, the parent/legal guardian will assist to complete the questionnaire on their behalf. The subject's parent/legal guardian will also complete a questionnaire on Week 12 or Early Termination (as applicable) for their assessment of acceptability of the formulation the subject received.

Acceptability and palatability will be assessed by numeric response marked on line between numbers 0-100 (higher scores indicate better acceptability and/or palatability) in response to questions about how the study drug tasted, how easy it was to swallow the study drug, and, for those who received that tablet formulation, how they felt about the number of tablets they had to swallow.

Responses to the acceptability and palatability questionnaire by subjects and their parent/legal guardian at Day 1, Week 12 and Early Termination (as applicable) will be respectively summarized by formulation (ie, SOF/VEL FDC400/100 mg adult tablet, 200/50 mg low dose tablets and oral granules) and by dose (SOF/VEL 400/100 mg tablet, SOF/VEL 200/50 mg, SOF/VEL 150/37.5 mg) for each age group using the numbers and percentages of subjects in the following categories, as applicable:

- Did not taste the study drug (for question regarding study drug taste only)
- Score marked > 60 to 100
- Score marked 40 to 60
- Score marked 0 to < 40

A by-subject listing of acceptability and palatability of SOF/VEL FDC will be provided by subject ID number in ascending order.

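### The Day 1 acceptability questionnaire is listed both before dosing and directly after the first dose, and the SAP has no rule to separate the two

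*Protocol*

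**What the plan says.** The Day 1 visit is described in two consecutive parts of the protocol, and the questionnaire appears in both.

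- **Section 6.2.2 (Day 1 Assessments)** opens with the rule that "the following tests and procedures must be completed prior to enrollment and dosing/dispensing on Day 1". One of the items under it is "SOF/VEL Acceptability Questionnaires".
- **Section 6.2.2.1 (Drug Administration)** runs in this order: swallowability test if still outstanding, dispensing, instruction, then "Observe the subject taking the first dose of study drug (with or without food) and record the time of first dose", then "Subject or parent/legal guardian (as applicable) will complete the relevant acceptability questionnaires".

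The procedures tables in Protocol Appendix 2 mark the questionnaire at Day 1. Footnote i of Appendix Table 1, attached to the Day 1 column, says "Day 1 assessments must be performed prior to dosing". Footnote j of Appendix Table 2 contains the same sentence. SAP Appendix 1 reproduces both tables and both footnotes.

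On content, Protocol Section 6.10.7 says that "a questionnaire will be administered to subjects to assess acceptability and palatability of the formulation they received on Day 1", with Week 12 and Early Termination as the other occasions. SAP Section 7.10 says the scores are given "in response to questions about how the study drug tasted, how easy it was to swallow the study drug" and, for tablets, about the number to be taken. It summarises Day 1 by formulation and dose within each age group, in three score bands plus a category for not having tasted the drug.

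**The concern.** The same form is given two places in one visit, and they conflict. The only explicit timing instructions, in Section 6.2.2 and the footnotes, place it before dosing. Its questions can be answered only after dosing. A site that follows the explicit rule collects scores with no experience of the drug behind them. A site that follows both sections may collect the form twice.

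Acceptability, including palatability, is a stated secondary objective of the Treatment Phase (Protocol Section 2) and a secondary endpoint (Sections 3.1 and 8.1.3). It matters most for the granules, which Section 5.2.1 says are taste-masked because the active ingredients are bitter. If pre-dose and post-dose forms are pooled, the Day 1 table for each formulation mixes ratings of the drug with guesses, and nothing in the SAP would show it.

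**Working it through.** No arithmetic applies, because the point concerns the order of procedures. The check sets the texts side by side.

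| Source | Placement of the Day 1 questionnaire | Explicit about timing? |
|---|---|---|
| Protocol 6.2.2 | Before enrollment, dispensing and dosing | Yes |
| Protocol Appendix Table 1, footnote i (Day 1 column) | Before dosing | Yes, for Day 1 assessments in general |
| Protocol Appendix Table 2, footnote j | Before dosing | Same sentence, but as extracted it is not attached to the Day 1 column |
| Protocol 6.2.2.1 | Next item after the observed first dose | No; by list position only |
| Protocol 6.10.7 | Concerns the formulation received | No; implied by content |
| SAP 7.10 | Past-tense questions on taste and swallowing | No; implied by content |

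**Step 1. Can the two listings be read as one?** The swallowability test also appears in both sections, but each time with a condition that it is done only if not done before. The questionnaire carries no such condition. Read literally, it is therefore due twice, or due at whichever point the site chooses.

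**Step 2. What could a pre-dose form contain?** Before dosing, a child aged 6 or over may have taken a placebo tablet for the swallowability test, which Section 6.2.2 lists immediately ahead of the questionnaire. Any rating would then be of the placebo or a guess. Children aged 3 to < 6 receive granules, and Section 6.10.7 provides no placebo for that formulation, so they would have nothing to rate.

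**Step 3. Would the SAP catch it?** Section 7.10 does not restrict Day 1 to post-dose forms. Its category for not having tasted the drug could absorb some pre-dose answers, but it applies to the taste question only. Pre-dose answers on swallowing or number of tablets would fall into the score bands unmarked.

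**Step 4. Could it be sorted out afterwards?** Section 6.2.2.1 requires the time of the first dose to be recorded. Neither document says that the completion time of the questionnaire is recorded. Without it, pre-dose and post-dose forms cannot be told apart from what the documents require.

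**The case against.** The strongest reply is that the intention is clear. In Section 6.2.2.1 the questionnaire directly follows the observed dose, Section 6.10.7 speaks of the formulation received, and the SAP's questions are in the past tense. Sites may well do the sensible thing. The footnotes also cannot be meant for every Day 1 row, since the same column contains dispensing and the dosing diary. The instrument, the eCRF and the study procedures manual are not among the documents and may settle the timing. All of this stands as evidence of intent. It does not remove a mandatory instruction to the contrary.

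Four stronger readings are tempting and are not supported:

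- **That children are asked about taste before they have taken the drug.** A reader of Section 6.2.2 alone might infer this. Section 6.2.2.1 shows that the plan also places the form after the dose, so the defect is a contradiction and not a settled pre-dose design.
- **That all of the roughly 200 Day 1 forms are affected.** This would need every site to ignore Section 6.2.2.1. The documents give no basis for any count.
- **That the duplicate-record rules of SAP Section 3.7.3 would average two Day 1 scores or keep the more favourable one.** SAP Section 7.10 does not invoke Section 3.7.3, whereas Sections 7.2.1, 7.3 and 7.4 do. No analysis window is defined for questionnaires. Where times exist, the baseline rule takes the last record, which would be the post-dose one.
- **That children who stop because of taste would otherwise go unrecorded.** They have a questionnaire scheduled at Early Termination.

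**Conclusion.** The protocol contradicts itself on when the Day 1 questionnaire is completed, and the SAP has no rule to separate the resulting forms. Any form completed before the first dose is uninterpretable for taste, swallowing and tablet burden.

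The size is limited. It concerns one of the two scheduled readings for a child who completes treatment (Day 1 and Week 12), on a secondary endpoint that is summarised descriptively with no inference. Week 12 and Early Termination responses, the primary safety and PK analyses and SVR12 are not touched, so palatability of the granules can still be assessed from the later forms.

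The conclusion assumes that the questionnaire's content is as SAP Section 7.10 describes it, and that no document outside the protocol and SAP overrides Section 6.2.2. The correction is worth making because the endpoint is a stated one and the repair is cheap.

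**What to change.** In the protocol:

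- Delete the acceptability questionnaires from the pre-dose list in Section 6.2.2.
- State in Section 6.2.2.1 that they are completed after the first dose has been taken.
- Exempt them from the pre-dose sentence in footnote i of Appendix Table 1 and footnote j of Appendix Table 2, and carry this into the copy in SAP Appendix 1.
- Record the completion time of the Day 1 questionnaire, or a before/after-dose flag.

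In SAP Section 7.10, summarise only Day 1 questionnaires completed after the first dose, and list pre-dose forms and forms of unknown timing separately.

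The cost is amended wording, notice to sites and one extra data item. No visit or procedure is added. The downside is that some forms already collected may drop out of the Day 1 summary because they were completed before dosing or their timing cannot be established.

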6.2.2.1. Drug Administration

The following procedures/assessments are to be completed at this visit:

- Perform SOF/VEL FDC swallowability assessment (if not previously completed at screening).
- Dispense study drug(s) as directed by the IWRS
- Instruct the subject on the packaging, storage, administration of study drug, and provide dosing diary and instructions.
- Observe the subject taking the first dose of study drug (with or without food) and record the time of first dose.
- Subject or parent/legal guardian (as applicable) will complete the relevant acceptability questionnaires.

• CCI

6.3. PK Lead-in Phase: Treatment Assessments

6.3.1. Day 3 (Telephone Call)

The site staff will perform the following assessments over the telephone with the subject and/or subject's parent/legal guardian on Day 3:

- Assessment of AEs and concomitant medications
- Review Subject Dosing Diary with subject and/or subject's parent/legal guardian

6.3.2. Day 7 – Intensive PK (+3 days)

The Day 7 intensive PK visit should occur on the protocol-specified visit date based on the baseline visit. For the purposes of scheduling, the Day 7 intensive PK visit may be performed within +3 days of the protocol-specified visit date (subjects will continue daily dosing through the intensive PK Visit).

Subjects should come in a fasted state for the Day 7 intensive PK visit (i.e., no food or drink except water at least 8 hours prior to the Day 7 intensive PK visit). Subject and/or parent/legal guardians should be instructed that the Day 7 dose of SOF/VEL FDC must **not** be taken prior to the visit and until the evaluations listed below are completed.

If the subject has already dosed prior to the Day 7 clinic visit or is **not** in a fasted state, the Day 7 intensive PK assessments must not be completed. The subject and/or parent/legal guardians should be instructed to return in a fasted state within 3 days (Days 8, 9, or 10) for the intensive PK visit.

If dosing non-compliance is identified per Subject Dosing Diary or study drug count on or prior to the Day 7 visit, the Day 7 intensive PK assessments must not be completed. The subject and/or parent/legal guardians should be counseled regarding proper dosing and be scheduled to return for the Day 7 intensive PK visit no sooner than 3 days following compliant dosing and no later than Day 11 (i.e., return on Day 10 or Day 11). If dosing non-compliance is due to an AE, consultation with the Gilead Medical Monitor is required regarding the potential of rescheduling the Day 7 intensive PK visit.

In both scenarios described above, the subject should be reminded or the parent/legal guardian should be reminded that the subject should not to take the SOF/VEL FDC prior to arriving at the clinic on the day of the re-scheduled intensive PK visit. All Day 7 intensive PK assessments listed below should be completed when the subject returns.

The following evaluations are to be completed at the Day 7 intensive PK visit:

- Perform a symptom-directed physical examination
- Vital signs
- Body weight and height

- Assessment of AEs and concomitant medications
- Perform study drug accountability
- Review Subject Dosing Diary
- Obtain blood samples for:
 - Hematology
 - Chemistry
 - Coagulation tests
 - HCV RNA
 - Viral sequencing (archive)
- Obtain urine samples for the following procedures:
 - Urine pregnancy test (females of childbearing potential only). If the urine pregnancy test is positive, the intensive PK sampling will not be completed. The positive result will be confirmed with a serum pregnancy test.
 - Urinalysis
- Perform intensive PK sampling:
 - Blood samples will be collected at 0 (predose, ≤ 30 minutes prior to dosing). After collection of the predose sample, subjects will be provided a standardized meal. Within 5 minutes after consuming the standardized meal, subjects will be dosed with SOF/VEL FDC per dosing requirements.
 - Postdose blood samples will be collected as follows:
 - For Cohorts 1 and 2: 0.5, 1, 2, 3, 4, 6, 8, and 12 hours postdose (with predose also serving as $t = 24$).
 - For Cohort 3 only: 0.5, 1, 2, 3, 4, 8, and 12 hours postdose (with predose also serving as $t = 24$).
 - Subjects will be restricted from food intake until after collection of the 4-hour postdose blood sample, except for subjects in Cohort 3. Please also refer to the PK manual for details about standardized meals and PK sample processing instructions.

After completing the Day 7 intensive PK visit subjects will then continue to the Week 4 visit in Treatment Phase (described in Section 6.5.2) with no interruption in dosing.

6.4. Treatment Phase: Treatment Assessments

6.4.1. Weeks 1 (\pm 3 days)

Subjects who participated in the PK Lead-in will start study visits in the Treatment Phase at Week 4.

The following procedures/assessments are to be completed at this visit:

- Perform symptom-directed physical examination
- Vital signs
- Body weight and height
- Assessment of AEs and concomitant medications
- Review Subject Dosing Diary
- Obtain blood samples for:
 - Hematology
 - Chemistry
 - Coagulation tests
 - HCV RNA
 - Viral sequencing (archive)
 - Single sparse PK sample collected anytime

6.4.2. Weeks 4 and 8 (\pm 3 days)

CCI

The following procedures/assessments are to be completed at this visit:

- Perform symptom-directed physical examination
- Vital signs
- Body weight and height
- Assessment of AEs and concomitant medications

- Obtain blood samples for:
 - Hematology
 - Chemistry
 - Coagulation tests
 - HCV RNA
 - Viral sequencing (archive)
 - Two sparse PK samples collected at Week 4 and Week 8, predose and between 15 minutes and 4 hours postdose CCI [REDACTED]
 - HBV DNA testing for subjects HBcAb positive at Screening
- Obtain urine sample for:
 - Urine pregnancy test for females of childbearing potential only
- Review medication compliance with subject and/or parent/legal guardian (subject should return all study drug at these visits)
- Review Subject Dosing Diary
- Dispense study drug as directed by the IWRS

